6.2.5. Overall Survival

Overall survival (OS) will be presented in months and is defined as the duration in months from the date of first pomalidomide dose to the date of death (any cause). Subjects who are alive at the time of analysis will be censored at the last known time that the subject was alive. Overall survival will be summarized by median survival time along with the corresponding 95% CI, calculated using Kaplan-Meier methods (the estimate of variance will be calculated using Greenwood's formula) ([Kaplan and Meier, 1958](#)) for each tumor type/disease indication separately. The Kaplan-Meier curve for survival will be presented graphically. The number and percentage of total deaths will be summarized. The survival rate at 3, 6, 9, 12, 18, and 24 months will be reported and the corresponding standard error provided.

Due to the low anticipated number of subjects and events/censoring, additional summary statistics will be provided, including the arithmetic mean, median, StdDev, Q1, Q3, Min, and Max values.

In addition to presentation of OS analysis data, descriptive statistics (arithmetic mean, median, StdDev, Q1, Q3, Min, and Max values) for follow-up time shall be presented for all subjects regardless of survival status, and for only subjects alive at the time of the analysis. Follow-up is defined as the duration in months from the date of first pomalidomide dose to the date of death (any cause), or last known time the subject was known to be alive if alive at the time of analysis or lost to follow-up. Analyses will be based on the ITT Population and/or Safety Population. The ITT Population will not be used should all enrolled subjects have received at least one dose of study drug.

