12. PRIMARY AND END OF STUDY FINAL ANALYSES

All tables, listings and figures detailed in this SAP will be provided for the primary final analysis that will be conducted when all on treatment subjects will have completed their 28-Day Post Treatment Safety Follow-up visit, 28 days post last dose of pomalidomide.

For the end of study final analysis, all outputs will be rerun once all subjects will have discontinued the follow-up period (up to 5 years after the last subject enrollment date).

REFERENCES

Brookmeyer R and Crowley J. A confidence interval for the median survival time. *Biometrics* 1982;38:29-41.

Kaplan E L and Meier P. Nonparametric estimation from incomplete observations. *Journal of the American Statistical Association* 1958;53(282):457-481.

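### SAP 6.2.5 defines follow-up time so that it equals observed survival time; the all-subjects row cannot show how long subjects could have been observed

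*SAP*

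**What the plan says.** SAP 6.2.5 measures OS in months, "defined as the duration in months from the date of first pomalidomide dose to the date of death (any cause"), and for survivors states: "Subjects who are alive at the time of analysis will be censored at the last known time that the subject was alive". Results are given per tumor type as a Kaplan-Meier median, a curve, the number and percentage of deaths, and rates at 3 to 24 months with standard errors. Mean, median, standard deviation, quartiles and range of OS are added because numbers are small.

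The same section then asks for those descriptive statistics "for follow-up time shall be presented for all subjects regardless of survival status, and for only subjects alive at the time of the analysis". The definition begins "Follow-up is defined as the duration in months from the date of first pomalidomide dose to the date of death (any cause") and continues, for everyone else, "or last known time the subject was known to be alive if alive at the time of analysis or lost to follow-up".

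SAP 12 runs the outputs twice: at a primary analysis, "when all on treatment subjects will have completed their 28-Day Post Treatment Safety Follow-up visit", and again when all subjects have left follow-up, up to 5 years after the last enrolment. Neither document plans a reverse Kaplan-Meier or potential follow-up summary, and neither states an expected length of follow-up.

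**The concern.** A follow-up figure tells the reader how long subjects could have been observed, and so how far the survival rates rest on observation rather than censoring. To do that, it should depend on enrolment and cut-off dates, not on how soon subjects died. The SAP presents follow-up as something additional to OS, but its definition yields the same variable.

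Long-term efficacy is a secondary objective, and OS rates are reported to 24 months in each stratum. Under this definition, two strata with identical enrolment and cut-off dates show different follow-up if their mortality differs, and the one with worse survival looks less followed. In a high-mortality stratum the figure would also barely change between the primary and end-of-study runs, despite years of added observation.

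**Working it through.** **1. The two definitions side by side (SAP 6.2.5)**

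| | OS | Follow-up, all subjects |
|---|---|---|
| Start | first dose | first dose |
| End, if died | date of death | date of death |
| End, otherwise | last known alive | last known alive |

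Let T be time from first dose to death and C time from first dose to cut-off. Ignoring losses, and taking survivors as known alive at cut-off, both columns are X = min(T, C). OS analysis also uses the death indicator; the follow-up row does not. Potential follow-up is C. This identity needs no assumption about survival.

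**2. Inputs for the size**

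There is no stated follow-up figure to reproduce. From the documents:
- Up to 20 evaluable subjects per stratum (Protocol 9.3). The Simon design behind this reproduces: exact alpha 0.035, power 0.902.
- Stage lengths of about 18 and 27 months (Protocol 3.2), together 45.
- At most 24 cycles of 28 days. With the 28-day visit, (672 + 28)/30.4375 = 23.0 months, ignoring cycle delays.
- Final run up to 60 months after last enrolment (SAP 12).

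Assumed, because the documents do not give them: exponential survival with median m; uniform accrual over A months; cut-off d months after last enrolment; no losses. Protocol 1.1.1 gives one median OS for a study tumor type, about 9 to 12 months for diffuse intrinsic brain stem glioma, as general prognosis and not after recurrence.

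**3. Formulas** (λ = ln 2/m; C uniform on d to d + A)

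- Median potential follow-up: d + A/2.
- Median of the all-subjects row: P(X > x) = exp(−λx) for x ≤ d, so the median is m whenever m ≤ d. If m > d, it solves exp(−λx)(A + d − x)/A = 0.5.
- Proportion alive at cut-off: p = [exp(−λd) − exp(−λ(d + A))]/(Aλ).
- Among survivors, C has density proportional to exp(−λc), which favors small C, that is, late enrollees.

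**4. Example: m = 9, A = 45, d = 23**

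- λ = 0.0770.
- All-subjects median: 9.0 months, since 9 < 23.
- Potential follow-up: 23 + 22.5 = 45.5 months.
- p = (0.1701 − 0.0053)/(45 × 0.0770) = 0.0475, or 0.95 of 20 subjects.
- Chance of no survivor in 20: (1 − 0.0475)^20 = 0.38.
- Survivors-only median: 31.6 months.

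**5. Other settings** (A = 45)

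| m | d | All-subjects median | Potential median | Expected alive of 20 | Survivors-only median |
|---|---|---|---|---|---|
| 6 | 3 | 5.5 | 25.5 | 2.7 | 9.0 |
| 9 | 3 | 7.6 | 25.5 | 4.4 | 11.6 |
| 12 | 3 | 9.4 | 25.5 | 6.0 | 13.8 |
| 6 | 23 | 6.0 | 45.5 | 0.3 | 29.0 |
| 12 | 23 | 12.0 | 45.5 | 1.9 | 33.8 |
| 9 | 60 | 9.0 | 82.5 | 0.06 | 68.6, usually empty |

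As m runs from 3 to 24 at d = 23, the all-subjects median runs from 3.0 to 23.6 while potential follow-up stays at 45.5.

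Median potential follow-up from d + A/2:
- Stratum closed after Stage 1, primary analysis (A 12 to 18, d 3 to 23): 6 + 3 = 9 to 9 + 23 = 32 months.
- Both stages, primary analysis (A 39 to 45, d 3 to 23): 22.5 to 45.5 months.
- End of study, d = 60 (A 12 to 45): 66 to 82.5 months.

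The gap can be small. For a stratum closed after Stage 1 with A = 12, d = 3 and m = 12, it is 6.3 against 9.0 months.

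**The case against.** A reader might infer that the trial will report about 6 to 12 months of follow-up when subjects were observable for about 3 to 4 years. The documents do not support that. The first range only returns an assumed median OS of 6 to 12 months. The second needs a stratum that completes both stages and a last subject who stays on treatment close to 24 cycles. At the design's 10% null rate a stratum closes after Stage 1 with probability 0.9^9 + 9 × 0.1 × 0.9^8 = 0.77. Stage lengths are also not accrual lengths: the 18 months run to the Stage 1 decision, and Protocol 9.8 suspends enrolment for the interim. At the end-of-study run, potential follow-up is 5 years or more if that period runs in full.

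It is also tempting to say that the maturity of the OS results cannot be judged. That goes too far. SAP 6.2.5 already requires death counts, Kaplan-Meier curves and landmark rates with standard errors, and in the late cut-off settings nearly all subjects have died, which itself shows maturity. No planned analysis compares strata.

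Finally, the row is explicitly defined, and a survivors-only version is planned. The definition is clear, but the label does not fit it. The survivors-only row helps when many are alive; where mortality is high it describes few or no subjects, mostly late enrollees.

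**Conclusion.** The point holds as one of labelling and omission. The all-subjects follow-up row is observed OS time under another name, and this follows from the SAP text alone. The row therefore falls with mortality and understates potential follow-up, and no planned table supplies the missing quantity.

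The direction is certain wherever subjects die before cut-off; the size is not. About 9 against 45 months is an illustration that rests on median OS 9 months, 45 months' uniform accrual, exponential survival, a cut-off 23 months after last enrolment and no losses. The documents give no median OS for recurrent disease and fix neither the accrual pattern nor the cut-off date.

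The effect is confined to a descriptive table. OS Kaplan-Meier estimates, the primary endpoint and the Simon decision rule do not change. It would be good to correct, but nothing depends on it.

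**What to change.** In SAP 6.2.5, for each stratum and at both the primary and end-of-study analyses:

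- Add median follow-up by reverse Kaplan-Meier (deaths treated as censored, end of observation as the event), or the median and range of time from first dose to data cut-off for every subject, without shortening.
- Report with it the number alive and the number lost or withdrawn.
- Keep the all-subjects row, relabelled as observed time on study, and keep the survivors-only row with its denominator shown.

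The two options should not be mixed by running deaths to the cut-off while shortening losses and withdrawals. Only living subjects can be lost, so that hybrid would make a stratum with worse survival look better followed.

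The cost is one or two SAP sentences, one derived variable and one table row; the SAP already uses the dates needed. The reverse Kaplan-Meier median will be imprecise, or not estimable, when few subjects are alive, and the simple time to cut-off is then the more useful figure.

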6.3. Subgroup Analysis

There are no subgroup analyses planned to be conducted.

6.4. Pharmacokinetic Analysis

6.4.1. Handling of Pharmacokinetic Data

Posttreatment concentrations that are below the limit of quantitation (BLQ) will be treated as missing. Concentrations assigned a value of missing will be omitted from the descriptive statistics. A concentration value of zero will be excluded from the computation of the geometric

mean (geometric CV%). Geometric CV(%) is calculated as follows: $CV(\%) = 100 \times \sqrt{\exp(V) - 1}$, where V denotes the variance of the log-transformed values.

If any subjects are found to be noncompliant with respect to dosing, have incomplete data, or encounter other circumstances that would affect the evaluation of PK, a decision will be made on a case-by-case basis as to their inclusion in the PK analysis. Data excluded from PK analysis will be included in the data listings, but not in the summaries.

In tables and listings for the derived PK data, there should be four decimal places for numerical values below 1, three decimal places for numeric values below 10 but above 1, and two decimal places for numeric values above 10. However, the listings of raw data should not have more or fewer decimal places than the actual data.

6.4.2. Presentation of Pharmacokinetic Results

Listings of PK blood sample collection times, derived sampling time deviations, drug concentrations, and PK parameters will be provided by subject in the PK population.

Plasma concentrations for pomalidomide will be summarized by nominal time points or collection intervals, including sample size (N), mean, StdDev, CV%, geometric mean, geometric CV%, Min, median, and Max. Mean (\pm StdDev) and individual plot of pomalidomide plasma concentrations versus time will be presented in both linear scale and semi-logarithmic scale.

6.4.3. Population Pharmacokinetic Analysis

Pomalidomide concentration data from this study may be combined with the concentration data from other pediatric studies and literature data to perform a population PK analysis. The between-subject variability for PK parameters may be estimated. If data allow, main PK parameters (clearance and volume of distribution) may be summarized by age as appropriate (eg, ≥ 1 years to < 6 , ≥ 6 to < 12 , and ≥ 12 years).

6.5. Interim Analysis

Each tumor type/disease indication incorporates the Simon's Optimal Two-stage study design, using a 5% significance level, 90% power, and a lower and upper boundary of 10% and 40%, respectively, for the primary endpoint. For stage one to be evaluated in a given tumor type/disease indication, there must be 9 subjects eligible for the primary endpoint analysis. Subjects If at least 2 subjects are observed as having as either a CR, PR or long-term SD according to central response review, ie, at least 2/9 ($\geq 22\%$), then enrollment in to stage two will continue as planned; otherwise that tumor type/disease indication will be closed to enrollment and the treatment in that tumor type/disease indication considered inefficacious.

If, in a given tumor type/disease indication, none of the first 8 subjects evaluable for the primary endpoint have an OR or long-term SD before the ninth subjects is enrolled, that particular tumor type/disease indication will close to enrollment due to early identification of futility. Similar, if at the time of the interim analysis the required number of subjects observed with an OR or long-term SD is 5 or more, then the enrollment to that given tumor type/disease indication may to stopped due to the required efficacy across stage 1 and stage 2 to declare the study positive in that tumor type/disease indication having been demonstrated early. Each tumor type/disease

indication is run in parallel to each other meaning the interim analysis per tumor type/disease indication may be conducted at different times, as and when the data becomes available for analysis.

CELGENE PROPRIETARY INFORMATION

7. SUMMARY OF SUBJECT DISPOSITION

The disposition of subjects will be summarized with counts and percentages by tumor type/disease indication and in aggregate. Summaries will include the following:

- Number of Subjects Enrolled, Completed, and Discontinued;
- Number of Subjects in the various analysis population;
- Primary reasons for discontinuation from the treatment, from study, or during follow-up. The reasons for discontinuation should be consistent with the eCRF. This may be done for the ITT Population and Safety populations separately if needed.

A summary table of analysis population will present counts and percentages of the number of subjects by tumor type/disease indication and in aggregate that form the following analysis populations:

- Informed Consent/Assent Population;
- Intent-to-treat Population;
- Response Population;
- Safety Population;
- Pharmacokinetic Population.

A summary table of subjects enrolled by country, and site number will be provided for the ITT Population.

A summary table showing subjects that did not enroll into the study, and reason for non-enrollment, will be provided by tumor type/disease indication for the Informed Consent/Assent Population.

Reasons for completing / discontinuing the Screening Period will be collected on the Disposition – Screening eCRF and will be summarized by tumor type/disease indication and in aggregate for the Informed Consent/Assent Population with the following categories:

- Completed;
- Screen failure;
- Death;
- Adverse event;
- Pregnancy;
- Withdrawal by subject;
- Withdrawal by parent/guardian;

- Lost to follow-up;
- Study terminated by sponsor;
- Protocol violation;
- Physician decision;
- Other.

Reasons for completing / discontinuing the study Treatment Period will be collected on the Disposition – Treatment eCRF and will be summarized by tumor type/disease indication and in aggregate for the ITT Population, the Response Population and the Safety Population with the following categories:

- Completed;
- Death;
- Adverse event;
- Pregnancy;
- Progressive disease;
- Lack of efficacy;
- Recovery;
- Withdrawal by subject;
- Withdrawal by parent/guardian;
- Non-compliance with study drug;
- Lost to follow-up;
- Study terminated by sponsor;
- Protocol violation;
- Physician decision;
- Disease relapse;
- Transition to commercially available treatment;
- Other;
- Site terminated by sponsor.

Reasons for discontinuing the study Follow-up Period / study will be collected on the Disposition – Follow-up eCRF and will be summarized for the ITT Population, the Response Population and the Safety Population with the following categories:

- Completed;

- Death;
- Adverse event;
- Pregnancy;
- Progressive disease;
- Withdrawal by subject;
- Withdrawal by parent/guardian;
- Lost to follow-up;
- Study terminated by sponsor;
- Protocol violation;
- Physician decision;
- Disease Relapse;
- Transition to commercially available treatment;
- Other.

Listings will be provided showing all subjects with signed informed consent/assent showing their status for each study period.

8. DEMOGRAPHICS AND BASELINE CHARACTERISTICS

Demographics and baseline characteristics will be summarized by the ITT Population and the Safety Population per tumor type/disease indication and in aggregate, while medical and treatment histories will be summarized by tumor type/disease indication and in aggregate for the Safety Population; only the Safety Population will be used if all enrolled subjects receive at least one dose of study drug. Baseline clinical characteristics are defined as the latest data collected on or before Cycle 1 Day 1, but before start of treatment. Individual subject listings will be provided to support the summary tables.

8.1. Demographics

Age (years), height, and weight at baseline will be summarized using descriptive statistics (n, mean, median, StdDev, Q1, Q3, Min, and Max). Age category (≥ 1 years to < 6 years, ≥ 6 years to < 12 years, ≥ 12 years), gender, race, ethnicity, and other categorical variables will be summarized by frequency tabulations.

Age will be calculated as follows: $\text{age (year)} = [(\text{Date of informed consent/assent} - \text{Date of Birth} + 1) / 365.25]$. In the table, age will be presented as an integer. In the listing, age < 2 years will be displayed in month(s), which will be calculated as $\text{age (month)} = \text{Integer} \leq [(\text{Date of informed consent/assent} - \text{Date of Birth} + 1) / 30.4375]$. Years reached are to be used for categorization.

Use of corticosteroid use at baseline, taken from the Concomitant Medications of Special Interest CRF form, will be indicated in the summary table as well as its use as either physiologic dosing or therapeutic dosing will be presented. Physiologic dosing is defined as no more than $0.75 \text{ mg/m}^2/\text{day}$ of dexamethasone or equivalent.

Within listings, age will be displayed in years and months as computed following directions given in [Appendix 1A, Section 48](#), while within tables summary statistics for age in years will be used.

Body surface area (BSA) will not be recalculated for tables, listings, and graphs (TLG) presentation but presented based on BSA as calculated and reported by the site per their institutional practice.

8.2. Baseline Disease Characteristics

Baseline disease characteristics will be summarized. Continuous variables will be summarized using descriptive statistics (n, mean, median, StdDev, Q1, Q3, Min, and Max). Categorical variables will be summarized with counts and percentages.

The number and percentage of subjects in each of the following categories will be presented:

- Lansky/Karnofsky performance status at baseline (the 2 performance assessments will be presented separately);
- Tumor type.

8.3. Medical History

A summary of medical history will be presented by Medical Dictionary for Regulatory Activities (MedDRA) version 21.0 or higher system organ class (SOC) and preferred term (PT) for the Safety Population.

Medical and surgical history will be sorted in descending frequency of the SOC based on the aggregate column, and by PT within each SOC; if counts tie, then further by alphabetical order.

8.4. Prior Concomitant and Subsequent Medications/Procedures

Medications initiated prior to the start of study treatment and continued after the start of study treatment will be counted as both prior and concomitant medications.

Tables and listings described in this section will use either the ITT Population or the Safety Population.

8.4.1. Prior Medications and Procedures

Prior medications, therapies and procedures, such as surgeries and transplants, are defined as medications or procedures that were started before the start of the study treatment and either ended before the start of the study treatment or continued after study treatment start. A summary showing the number and percentage of subjects who took prior medications will be presented for the Safety Population by tumor type/disease indication and in aggregate.

Prior medications collected on the “Prior and Concomitant Medication” eCRF page, prior procedures collected on the “Prior and Concomitant Procedures” eCRF page, and prior and concomitant anticancer therapies collected on the “Anticancer Therapies for Brain Tumor – Systemic (Prior)”, “Anticancer Therapies for Brain Tumor – Hormonal (Prior)”, “Anticancer Procedures for Brain Tumor - Prior Radiation Therapies”, “Anticancer Procedures for Brain Tumor - Prior Cancer Surgeries”, and “Anticancer Procedures for Brain Tumor - Prior Stem Cell Transplant” eCRF pages will be summarized.

The number of prior therapies and procedures, such as surgeries, will be summarized for prior radiation therapies, prior cancer surgeries, prior systemic anticancer therapies, prior stem cell transplants and other prior anticancer therapies by frequency tabulations based on the Safety Population. Descriptive statistics may be provided also, if needed. The therapies/surgeries with the same sequence/regimen number are counted as 1 prior therapy/surgery.

Prior anticancer therapies / medications will be summarized, if applicable, based on the therapeutic drug class [Anatomical Therapeutic Chemical (ATC) level 1] and preferred name, both based on WHODD March 2018 or later, sorted by frequency of ATC level 1 term and by preferred name within ATC level 1 terms, in the aggregate column; if counts tie, then further by alphabetical order. A table summarizing number of prior therapies and types of therapies will also be provided.

Prior procedures will be summarized, if applicable, based on the MedDRA, version 21.0 or higher, SOC and PT sorted by frequency of SOC and PT within SOC, in the aggregate column; if counts tie, then further by alphabetical order.

Individual listings of prior medications and procedures will be provided to support the tables.

